Participants will be randomized to receive either TQ Formula + Standard of Care (SOC) or placebo +SOC

Administer Study Intervention

Participants will be provided with study treatment kit, with enough capsules for 14 days of treatment, 3 capsules BID.

Concomitant Medications and Adverse Events Review

Participants will be assessed for any new adverse events and any changes in concomitant medications

Patient Reported Outcomes

Participants will receive the Modified FLU-PRO Plus questionnaire to complete on a daily basis for the duration of the study, from randomization to final study visit (Day 21).

Subsequent Study Visits (Including Day 21 Final Visit)

Concomitant Medications and Adverse Events Review

Participants will be assessed for any new adverse events and any changes in concomitant medications at each study visit

Physical Exam

A complete physical exam will be performed by the investigator or appropriately qualified designee and documented in the source and in the eCRF at Day 7 and Day 14. A complete physical examination, performed at screening and other specified visits, should include an evaluation of the head, eyes, ears, nose, and throat, and the cardiovascular, dermatologic, respiratory, gastrointestinal, and neurologic systems. Any abnormality identified at baseline should be recorded in the patient's medical records. Limited, symptom-directed physical examinations should be performed at specified postbaseline visits and as clinically indicated. Changes from baseline abnormalities should be recorded in patient notes. New or worsened clinically significant abnormalities should be recorded as adverse events in the patient's medical records.

Vital Signs

Vital signs, including blood pressure (BP), temperature and heart rate will be collected and documented in source and in the eCRF at each study visit.

Serum Collection (Blood sample for immune monitoring)

Blood samples (approximately 15 ml) will be collected for immune monitoring at Day 7 and Day 14, in addition to the baseline visit.

Sample for quantitative viral load testing (RT-PCR)

Participants will have a sample taken for RT-PCR quantitative viral testing at Day 7 and again at Day 14, in addition to the baseline visit.

Laboratory Evaluations (Hematology and Serum Chemistry)

Blood samples (approximately 10ml in total) will be taken for safety laboratory evaluations (as listed in screening above) at Day 7 and 14 and as clinically indicated at any other study visits

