9.2 SAMPLE SIZE DETERMINATION

For statistical analysis purposes, sustained clinical response is defined as a reduction to a score of ≤ 2 on all symptom scores on the Modified FLU-PRO Plus questionnaire.

Based on the median time to sustained clinical response reported by CDC [122], the expected median time to response in the placebo arm will be approximately 16 days from the onset of symptoms in outpatients. With a sample size of 20 in each arm, a difference in median time to sustained clinical response of 10 days between the intervention arm and the placebo arm will be able to be detected with 81.5% statistical power with 5% Type-1 error rate. Median time to sustained clinical response will be estimated based on 21-day follow-up. With an attrition expectation of around 20%, the planned accrual is 26 patients in each arm and potentially up to 30 patients.

Patients will be randomly assigned to one of the two study arms, using a block-randomization with a block size of 4, stratified by the enrolling sites. No other stratifications will be used. Randomization block size will be kept fixed at 4 as this is a small study and making the block size random as well is not needed. An unblinded statistician will generate a randomization list.

Definition of Evaluability for Primary Objectives: The double blind, placebo controlled two-arm clinical trial is designed to enroll up to 60 patients equally randomized between the two arms of the study. An evaluable patient is defined as a patient who has received at least one dose of the intervention drug or placebo.

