9.4 STATISTICAL ANALYSES

9.4.1 GENERAL APPROACH

Categorical variables will be presented as frequencies and percentages with column and row percentages in 2x2 or Rx C tables as appropriate. Association between two nominal variables will be investigated using Chi-Square tests and/or Fisher's Exact test as needed. Cochran Armitage trend-test may be included among the possible tests to investigate the possible trend between one ordinal factor and one binary factor. Association between two ordinal variables may be investigated through Non-zero Correlation test. Continuous variables will be presented as mean and standard deviation as well as five-number summary (minimum, first quartile, median, third quartile, and maximum). Range and inter-quartile range may also be explicitly provided as needed. Distribution of a continuous variable among the levels of a binary or polynomial factor will be investigated graphically through boxplots and through Wilcoxon-MannWhitney test and/or Kruskal Wallis tests. Association between two continuous variables will be described through scatter plots and Pearson's and Spearman's correlation coefficients as appropriate. When needed, normality assumption of a given continuous variable will be tested using Shapiro-Wilk Normality test. The details of the statistical models addressing each and every primary, secondary, and exploratory objectives along with primary predictors and control variables will be provided in a corresponding Statistical Analysis Plan (SAP). In this protocol document, a general analysis and statistical testing approach will be provided, and the details will be left for the study SAP.

In all comparisons and tests, a two-sided p-value will be used and a Type-1 error rate of 0.05 will be used to indicate significance. No multiplicity correction will be employed for statistical tests addressing the two primary objectives. Similarly, no multiplicity correction will be employed for statistical tests addressing the secondary and exploratory objectives as the results from these objectives must be considered within the hypotheses generating context.

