9.4.2 ANALYSIS OF THE PRIMARY EFFICACY ENDPOINT(S)

The primary endpoint of this clinical trial is the estimate of the median time to sustained clinical response for the treatment and placebo arms. Kaplan-Meier method will be used to estimate the time to sustained clinical response distribution and log-rank test will be utilized to compare the time to sustained clinical response distributions between the two study arms. Events will be defined as cases that attain clinical response while on the follow-up window and time to event will be calculated as the days from symptom onset to the resolution of symptoms to zero based on the Modified FLU-PRO Plus questionnaire. Patients who do not attain to clinical response while on the follow-up window will be censored on Day-21 or on the day they are off study before Day-21 due to other reasons. Although all analyses will be conducted based on the intent-to-treat context, sensitivity analyses based on the adherence to the protocol regimen will also be carried out for the primary as well as secondary objectives.

When appropriate, Last-Value-Carried-Forward (LVCF) imputation approach will be utilized for the missing values. As this is a small study that has a short span of enrollment and treatment windows, we do not anticipate excessive missing values; however, missingness structure will still be analyzed as to whether or not the missingness is Missing Completely at Random (MCAR), or Missing at Random (MAR), or Not-Missing at Random (NMAR). In the even of MCAR and MAR, sensitivity analyses will be carried out by using Multiple Imputation (MI) techniques.

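### The stated 81.5% power falls to about 77% under the plan's own Day-21 censoring (exponential times), and the primary event time has two stated origins with follow-up on a third clock

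*Protocol*

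**What the plan says.** **Sample size.** Protocol 9.2 expects a placebo median of about 16 days, counted from symptom onset. The target effect is "a difference in median time to sustained clinical response of 10 days between the intervention arm and the placebo arm". The protocol claims that, with 20 per arm, this effect "will be able to be detected with 81.5% statistical power with 5% Type-1 error rate". It adds: "Median time to sustained clinical response will be estimated based on 21-day follow-up". On losses: "With an attrition expectation of around 20%, the planned accrual is 26 patients in each arm and potentially up to 30 patients". SAP 3.2 repeats these figures. Neither document gives a distribution, hazard ratio, expected event count, formula or accrual pattern for the calculation.

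**Test.** Protocol 9.4.2 and SAP 5.3.2 specify a log-rank test. Protocol 9.4.1 says "a two-sided p-value will be used and a Type-1 error rate of 0.05 will be used to indicate significance".

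**Clocks.**
- Protocol 9.4.2: "time to event will be calculated as the days from symptom onset". SAP 5.3.2 also starts at onset.
- SAP 3.2 starts the same event time at the date of testing.
- Protocol 4.1 has the daily questionnaire completed "from randomization to final study visit (Day 21"), and SAP 6.3 counts Days 1 to 21 after randomisation.
- Protocol 9.4.2: "Patients who do not attain to clinical response while on the follow-up window will be censored on Day-21", or at an earlier exit. SAP 5.3.2 has the same rule.

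**Lag.** Inclusion criterion 3 asks only for recent symptoms and sets no maximum time since onset, so the onset-to-randomisation lag cannot be derived.

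**The concern.** The sample-size sentence combines an onset-based median with a follow-up limit that runs from randomisation, and it does not say how power was obtained. Power for a log-rank test depends on the number of events. If each patient is censored at Day 21 and the placebo median is 16 days, a substantial share of placebo patients contribute no event, so a calculation that ignores this will be too favourable.

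This sentence is the only justification of the sample size. A reader of a null result could not tell whether the trial was built to detect 10 days counted from onset, partly before treatment began, or a gain counted from randomisation. The unsettled origin also reaches the primary Kaplan-Meier and log-rank analysis, where SAP 3.2 and SAP 5.3.2 would give different times for the same patient.

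**Working it through.** **Inputs from the documents:** 20 per arm; placebo median 16 days; difference 10 days, so active median 6 days; 21-day limit; two-sided 0.05; log-rank test. **Assumed here, not stated:** exponential times, and medians on the same clock as Day 21. The hazard ratio (HR) is then 16/6 = 2.667, with natural log 0.981.

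**Step 1. How 81.5% can be reached.**
- All 40 patients counted as events, Freedman: Φ(√40 × (2.667 − 1)/(2.667 + 1) − 1.96) = Φ(0.915) = 82.0%.
- Uniform accrual over 4 or 5 weeks (the recruitment time in Protocol 5.5) plus 21 days minimum follow-up, two-sided log-rank: Lakatos 80.9% and 81.2%; simulation 81.2% and 82.0%.
- One-sided 5% with everyone stopped at Day 21: Freedman 80.3%, Lachin-Foulkes 81.2% (Schoenfeld overshoots, 85.3%).

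The first two routes credit events after Day 21, which Protocol 9.4.2 and SAP 5.3.2 censor. The third contradicts Protocol 9.4.1.

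**Step 2. The plan's own test and censoring.**
- Event probability by Day 21: 1 − exp(−ln2 × 21/16) = 0.597 for placebo; 1 − exp(−ln2 × 21/6) = 0.912 for active.
- Events: 20 × (0.5974 + 0.9116) = 30.2.
- Schoenfeld: Φ(√30.18/2 × 0.981 − 1.96) = Φ(0.734) = 76.9%.
- Freedman: Φ(√30.18 × 0.4545 − 1.96) = Φ(0.537) = 70.4%.
- Lakatos 76.3%; Lachin-Foulkes 72.2%; simulated log-rank 76.8% (20,000 runs).

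On this basis 81.5% needs about 34 events: 33.9/1.509 = 22.5, or about 23 per arm.

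**Step 3. Sensitivity (Schoenfeld, 20 per arm, Day-21 censoring).** For Weibull shape k, events use (21/median)^k, and log HR is k × ln(16/6).

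| Assumption | HR | Events | Power |
|---|---|---|---|
| Shape 0.9 | 2.42 | 29.4 | 66.8% |
| Shape 1.05 | 2.80 | 30.5 | 81.2% |
| 15.5 vs 5.5 days | 2.82 | 30.8 | 81.9% |
| 16.5 vs 6.5 days | 2.54 | 29.6 | 71.7% |

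**Step 4. Assumed onset-to-randomisation lag, effect acting only from randomisation.** The placebo median from randomisation is taken as 16 minus the lag. That subtraction is itself an assumption.

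| Lag | Medians | HR | Events | Power | Gain |
|---|---|---|---|---|---|
| 3 days | 13 vs 4.88 | 2.67 | 32.5 | 79.8% | 8.1 days |
| 4 days | 12 vs 4.50 | 2.67 | 33.3 | 80.7% | 7.5 days |
| 5 days | 11 vs 4.12 | 2.67 | 34.1 | 81.7% | 6.9 days |
| 3 days, 10-day gain kept | 13 vs 3 | 4.33 | 33.3 | 98.8% | 10 days |

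**Step 5. Planned accrual (base case of Step 2).** 21 per arm (26 × 0.8 = 20.8): 78.8%. 26: 86.7%. 30: 91.0%. With 26 per arm and 20% dropout spread over the 21 days: 36.3 events, 84.0%.

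**The case against.** The strongest reply is that 81.5% comes out of documented inputs: the recruitment time in Protocol 5.5 plus 21 days of follow-up gives 81-82% in a standard two-sided calculation. That stands as a likely origin of the figure, and it rules out calling it a miscalculation. It does not rescue the figure as the power of this analysis, because early enrollees are not followed beyond their own Day 21.

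A second reply is that the 77% rests on an unstated distribution and on putting an onset-based median on the Day-21 clock. This also stands. The protocol gives only an approximate 16 days, and half a day either way moves power to 82% or 72%. On the onset clock, with hazard ratio 2.67 throughout and Day 21 falling 21 days plus the lag after onset, assumed lags of 5, 7 and 9 days give 79.9%, 80.7% and 81.5%. That route credits the drug with time before treatment. At nine days, 19.4 of 33.9 expected events fall before randomisation, although inclusion criterion 5 requires scores of at least 3 on two symptoms.

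A reader might also infer that the primary event time has three origins. The documents write two, onset and testing; randomisation is the clock for follow-up and censoring. Both primary-analysis sections agree on onset, so the written contradiction about origin is between SAP 3.2 and those sections.

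**Conclusion.** The point holds in this form. The conflict of clocks is on the page and needs no modelling. The stated power does not hold under the plan's two-sided log-rank test with per-patient Day-21 censoring if times are exponential and the medians share that clock: about 77% (70.4% by Freedman), some 4 to 5 points below 81.5% by Schoenfeld or simulation. Other plausible inputs run from 67% to 82%, and higher if a 10-day gain is kept after a lag.

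Two stronger readings are not supported. One is that 81.5% is an arithmetic error: standard variants reach it, and the method is simply not given. The other is that the trial is seriously underpowered for its stated effect: in the base case, 26 per arm gives 86.7%, and 21 contributing per arm gives 78.8%. The text should be corrected; the sample size need not change on this ground. Confidence is medium, because the distribution and the lag are assumptions.

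**What to change.** Before unblinding, and without enrolling more patients:

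- **One origin.** Use randomisation for both the event time and Day-21 censoring in Protocol 9.2 and 9.4.2 and SAP 3.2 and 5.3.2. Keep time from symptom onset as a supportive summary.
- **Effect size.** Restate the placebo median on that origin with the assumed lag shown, and give the effect as a hazard ratio. Do not describe the onset-based 16 days as counted from randomisation.
- **Power.** Replace 81.5% with power under per-patient Day-21 censoring, naming method, distribution, sidedness and expected events, with a range over lag and shape. For 20 per arm, two-sided 0.05, Schoenfeld, hazard ratio 2.67 and exponential times: about 77% (30 events) if 16 and 6 days are taken on the same clock as Day 21; about 80-82% (32 to 34 events) for assumed lags of 3 to 5 days, with gains of 8.1 to 6.9 days. Weibull shapes 0.9 to 1.05 on the single-clock case give 67-81%.
- **Citation.** The 16 days cites entry 122, but the reference list ends at 116. This is a clerical correction only.

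The cost is text in four sections. The timing matters because the clock of the primary analysis changes. The stated power may be slightly lower, and times from randomisation will not compare directly with outside figures counted from onset.

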9.3 POPULATIONS FOR ANALYSES

- Full Analysis Dataset: The Full Analysis Set (FAS) is defined as all randomized participants who receive at least one dose of study intervention.
- Final Dataset for Primary Objectives (FDPO): FDPO is defined as all evaluable participants according to the evaluability definition above.
- Safety Analysis Dataset: The Safety Analysis Set is defined as participants who take at least one dose of study intervention.
- Per-Protocol Analysis Dataset: The Per-Protocol Analysis Set (PP) is defined as all participants in the FAS who complete all visits up to and including Day 14, are compliant with study medication and do not have any major protocol violation. Major protocol violations will be identified prior to breaking the blind.

9.4 STATISTICAL ANALYSES

9.4.1 GENERAL APPROACH

Categorical variables will be presented as frequencies and percentages with column and row percentages in 2x2 or Rx C tables as appropriate. Association between two nominal variables will be investigated using Chi-Square tests and/or Fisher's Exact test as needed. Cochran Armitage trend-test may be included among the possible tests to investigate the possible trend between one ordinal factor and one binary factor. Association between two ordinal variables may be investigated through Non-zero Correlation test. Continuous variables will be presented as mean and standard deviation as well as five-number summary (minimum, first quartile, median, third quartile, and maximum). Range and inter-quartile range may also be explicitly provided as needed. Distribution of a continuous variable among the levels of a binary or polynomial factor will be investigated graphically through boxplots and through Wilcoxon-MannWhitney test and/or Kruskal Wallis tests. Association between two continuous variables will be described through scatter plots and Pearson's and Spearman's correlation coefficients as appropriate. When needed, normality assumption of a given continuous variable will be tested using Shapiro-Wilk Normality test. The details of the statistical models addressing each and every primary, secondary, and exploratory objectives along with primary predictors and control variables will be provided in a corresponding Statistical Analysis Plan (SAP). In this protocol document, a general analysis and statistical testing approach will be provided, and the details will be left for the study SAP.

In all comparisons and tests, a two-sided p-value will be used and a Type-1 error rate of 0.05 will be used to indicate significance. No multiplicity correction will be employed for statistical tests addressing the two primary objectives. Similarly, no multiplicity correction will be employed for statistical tests addressing the secondary and exploratory objectives as the results from these objectives must be considered within the hypotheses generating context.

9.4.2 ANALYSIS OF THE PRIMARY EFFICACY ENDPOINT(S)

The primary endpoint of this clinical trial is the estimate of the median time to sustained clinical response for the treatment and placebo arms. Kaplan-Meier method will be used to estimate the time to sustained clinical response distribution and log-rank test will be utilized to compare the time to sustained clinical response distributions between the two study arms. Events will be defined as cases that attain clinical response while on the follow-up window and time to event will be calculated as the days from symptom onset to the resolution of symptoms to zero based on the Modified FLU-PRO Plus questionnaire. Patients who do not attain to clinical response while on the follow-up window will be censored on Day-21 or on the day they are off study before Day-21 due to other reasons. Although all analyses will be conducted based on the intent-to-treat context, sensitivity analyses based on the adherence to the protocol regimen will also be carried out for the primary as well as secondary objectives.

When appropriate, Last-Value-Carried-Forward (LVCF) imputation approach will be utilized for the missing values. As this is a small study that has a short span of enrollment and treatment windows, we do not anticipate excessive missing values; however, missingness structure will still be analyzed as to whether or not the missingness is Missing Completely at Random (MCAR), or Missing at Random (MAR), or Not-Missing at Random (NMAR). In the even of MCAR and MAR, sensitivity analyses will be carried out by using Multiple Imputation (MI) techniques.

9.4.3 ANALYSIS OF THE SECONDARY ENDPOINT(S)

None of the following endpoints depend on the findings of the primary endpoint.

The first secondary endpoint of this clinical trial is the differential change of viral load distribution overtime between the two-study arm. As the viral load will be measured at Baseline, on Day-7, and on Day-14 (and potentially for some patients in Day-4 and Day-10 visits), the outcome variable of interest will be a longitudinal interval-scale measure. To assess the differential behaviour of viral load overtime between the two study arms, Random Coefficients Models will be utilized where viral load will be the dependent variable and study arm and time will be main predictors. Viral load measures may be subjected to some data transformation (e.g., log transformation) to improve the model fit and assumptions as necessitated by model diagnostics. In addressing this objective, all available data will be utilized; that is, in addition to the evaluable patients, data from non-evaluable patients such as data only at baseline visit or data at baseline and Day-10 for example will be used to improve the local fit of the underlying model. To assess differential behavior in total symptom severity score, time*study-arm interaction will be investigated as well.

The percentages of RT-PCR negative/undetectable viral loads between the two study arms will be compared using Fisher's Exact test at Day-7 and Day-14 visits.

The third secondary endpoint of this clinical trial is the differential change of total and subdomain symptom severity score measured by Modified FLU-PRO Plus overtime between the two-study arm. As the total and subdomain symptom severity score will be measured at Baseline (Day-1) and on each day through Day-14, the outcome variables of interest will be a longitudinal interval-scale measures. To assess the differential behaviour of total and subdomain symptom scores overtime between the two study arms, Random Coefficients Models will be utilized where total and each of the subdomain symptom severity score will be the dependent variables and study arm and time will be main predictors. Total and subdomain symptom severity scores may be subjected to some data transformation (e.g., log transformation) to improve the model fit and assumptions as necessitated by model diagnostics. In addressing this objective, all available data will be utilized; that is, in addition to the evaluable patients, data from non-evaluable patients such as data only at baseline visit or data just at baseline and Day-10 for example will be used to improve the local fit of the underlying model. To assess differential behavior in total symptom severity score, time*study-arm interaction will be investigated as well. When scientifically indicated, aggregated symptom severity scores may be defined through combining a set of subdomains such as Nose, Eyes, And Throat.

Association between quantitative viral load and symptom severity will be investigated through regression models, where total symptom severity score will be the dependent variable predicted by the quantitative viral load measures in the model at each visit. Study-Arm*viral load interaction will be added to the model to investigate if any association between viral load and symptom severity is mitigated by the study treatment.

Last but not the least secondary endpoint is the comparison of Adverse Events (AE) and Serious Adverse Events (SAE) between the two study arms. AEs and SAEs are nominal variables described by grade and attribution to the protocol therapy. For the presentation purposes, we will define 'Toxicity' as an AE with at least possible attribution of the therapy. Summary tables of frequencies and percentages of AEs will be generated as number of episodes within number of patients (N-episodes/N-subjects) by grade and attribution. When frequencies allow, percentages of patients experiencing an AE, or a set of AEs will be compared between the two arms using Fisher's Exact test. In doing so, some aggregation can be done at the grade level such as 'Grade 3+' AEs or categories along these lines. Such comparisons will be done for toxicities of interest as well.

Analysis details for the exploratory aims will be provided in the study SAP.

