In an investigator-initiated, open-label-placebo and randomized controlled trial conducted from April 30 to July 29, 2020 in four medical care facilities in Pakistan, 313 COVID-19 positive patients were stratified into two groups: mild to moderate (cough, fever, sore throat, nasal congestion, malaise and/or shortness of breath) and severe (fever and/or cough along with pneumonia, severe dyspnea, respiratory distress, tachypnea (>30 breaths/min) or hypoxia ($SpO_2 <90\%$ on room air) (210 and 103 patients respectively) using the Clinical Management Guidelines for COVID-19 by the Ministry of National Health Services, Pakistan [114]. The patients within each of the two groups were randomly assigned to the treatment and control groups (Honey plus Nigella Sativa [HNS] and Placebo). The HNS group received honey (1 gm) plus Nigella sativa seeds (80mg) per kg body weight orally in 2-3 divided doses daily for upto 13 days while the control group received placebo (empty capsules). The primary outcomes were viral clearance (negative RT-PCR for the SARS-CoV-2 RNA), alleviation of clinical symptoms and the lowering of CGS on day 6. Secondary outcomes included reduction in fever degree (day 4), CRP levels (day 6), severity of symptoms (day 8), CGS score (day 10) and mortality on day 30. The study results showed that HNS helped with symptoms alleviation and viral clearance and reduced mortality in patients with moderate and severe disease. It was discovered that alleviation of COVID-19 symptoms for patients in the HNS groups occurred earlier than control groups: 4 versus 7 days for the moderate patients and 6 versus 13 days for the severe disease patients. Viral clearance (being negative for the SARS-CoV-2 RTPCR test) occurred 4 days sooner in the HNS group for both moderate and severe cases. A significant reduction in degree of fever was observed in the severe cases on day 4 (OR: 0.21; 95% CI: 0.09-0.46; P=0.0001). CRP levels decreased significantly ($P <0.0001$) on day 6 in both the HNS groups compared with their respective control groups. As per median degree of symptom severity on day 8, 98.13% patients were asymptomatic in HNS treated moderate cases in comparison to 56.31% in the control group (OR: 0.009; 95% CI: 0.001-0.08; $P <0.0001$). In severe cases, more patients were asymptomatic in the HNS group

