## Analysis plan for Secondary Aim-3:

Secondary estimand-3 is defined to be the difference of total and subdomain symptom scores measured through Modified FLU-PRO Plus questionnaire between participants taking 3 g TQ Formula (500 mg per capsule, 3 capsules BID) and participants taking placebo regardless of whether or not they actually receive their assigned therapy (ITT) and assuming that their hospitalization and treatment discontinuation rates will be similar. To address this estimand, the differential change of total and subdomain symptom severity score measured by Modified FLUPRO Plus overtime between the two-study arm will be estimated and compared between the two study arms. As the total and subdomain symptom severity score will be measured at Baseline (Day-1) and on each day through Day-14, the outcome variables of interest will be a longitudinal interval-scale measures. To assess the differential behaviour of total and subdomain symptom scores overtime between the two study arms, Random Coefficients Models will be utilized where total and each of the subdomain symptom severity score will be the dependent variables and study arm and time will be main predictors. Total and subdomain symptom severity scores may be subjected to some data transformation (e.g., log transformation) to improve the model fit and assumptions as necessitated by model diagnostics. In addressing this objective, all available data will be utilized; that is, in addition to the evaluable patients, data from non-evaluable patients such as data only at baseline visit or data just at baseline and Day-10 for example will be used to improve the local fit of the underlying model. To assess differential behavior in total symptom severity score, time\*study-arm interaction will be investigated as well. When scientifically indicated, aggregated symptom severity scores may be defined through combining a set of subdomains such as Nose, Eyes, And Throat. The above mentioned intercurrent events are applicable for Secondary estimand-1 as well. Therefore, hospitalization-free, while-on-study and per-protocol treatment versions of the above estimand will also be considered within each population definitions above. For the above analyses, the MIXED procedure of SAS software will be utilized.

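### The symptom-score analysis names only an arm-by-time term for differential benefit and does not fix the form of time or the deciding contrast; read as a linear slope, that term does not track speed of recovery

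*Protocol*

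**What the plan says.** The third secondary endpoint (Protocol 9.4.3) is the differential change in total and subdomain Modified FLU-PRO Plus scores, "measured at Baseline (Day-1) and on each day through Day-14". Random coefficients models are fitted with the scores as "dependent variables and study arm and time will be main predictors". The protocol then adds: "To assess differential behavior in total symptom severity score, time*study-arm interaction will be investigated as well". Scores "may be subjected to some data transformation (e.g., log transformation) to improve the model fit and assumptions as necessitated by model diagnostics".

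SAP 5.3.3, Aim-3, repeats this under PROC MIXED. It opens with "Secondary estimand-3 is defined to be the difference of total and subdomain symptom scores", and then says that "the differential change of total and subdomain symptom severity score measured by Modified FLUPRO Plus overtime between the two-study arm will be estimated". For viral load (Aim-1), with the same type of model, the SAP defines the estimand as a slope difference. For symptoms it does not use the word slope.

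Two other passages set the expected recovery times. Protocol 9.2 plans for "a difference in median time to sustained clinical response of 10 days between the intervention arm and the placebo arm", with a placebo median of about 16 days from symptom onset, hence 16 versus 6. Protocol 2.2.1 cites a COVID-19 trial of honey plus seeds with symptom relief at "4 versus 7 days for the moderate patients and 6 versus 13 days for the severe disease patients".

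Neither document mentions categorical days, curvature, an average or area under the curve, or how scores at the floor are handled.

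**The concern.** Item scores cannot go below 'Not at all' (Level-0 in SAP 7.9), and the plan expects many participants to improve well inside the 14-day window. A participant who reaches the floor early adds a flat run up to Day 14, and that run pulls a fitted straight line towards horizontal. Among recovered participants, a flatter slope can therefore mean faster recovery.

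The interaction is the only term the plan ties to differential behaviour. Once it is in the model, the arm coefficient (time counted from Day 1) is only the fitted Day-1 gap, so part of a real benefit would look like baseline imbalance. At stake is secondary hypothesis 3, which claims reduced duration and severity overall and in each domain. Depending on which term is reported, the same data could show a clear benefit, nothing, or an apparent slowing of decline.

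**Working it through.** The plan states no power or sample size for this endpoint. The 81.5% in Protocol 9.2 belongs to the primary log-rank test and is not used here.

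**Step 1. Is the slope monotone in recovery?** Take a score of 35 (assumed) falling linearly to zero R days after Day 1: y(d) = 35 x max(0, 1 - (d-1)/R), d = 1 to 14. The least-squares slope is b = sum[(d-7.5) y(d)] / sum[(d-7.5)^2], with denominator 14 x (14^2 - 1)/12 = 227.5. With complete, balanced data, the random-coefficients arm-by-time estimate is the difference in mean individual slopes.

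Example, R = 6: the numerator is -(35/6) x (39 + 27.5 + 18 + 10.5 + 5 + 1.5) = -(35/6) x 101.5 = -592.1, so b = -592.1/227.5 = -2.60.

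| Days to zero (R) | Slope per day | Mean score, Days 1-14 |
|---|---|---|
| 4 | -2.12 | 6.3 |
| 6 | -2.60 | 8.8 |
| 6.5 | -2.69 | 9.4 |
| 7 | -2.77 | 10.0 |
| 13 | -2.69 | 17.5 |
| 16 | -2.19 | 20.8 |

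The slope is steepest near R = 10 and flatter on both sides. At 6 versus 16 days its direction is right but the gap is small (0.41 per day), while the means differ by 12.0 points. At 4 versus 7 days the faster arm is flatter. At 6.5 versus 13 days the slopes tie.

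**Step 2. Where does the benefit go?** The fitted Day-1 value is the mean minus 6.5 x b. For R = 6 it is 8.75 + 6.5 x 2.60 = 25.7; for R = 16 it is 20.78 + 6.5 x 2.19 = 35.0. Both curves start at 35, so the model shows a Day-1 gap of 9.3 points that does not exist.

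**Step 3. How low are scores at response?** The documents give three readings. The main definition is every item <=2. SAP 5.3.2 requires all items below Level-2. Protocol 9.4.2 counts to resolution at zero. On the first reading a responder may still score well above the floor: Appendix 2 has 24 items, and 24 x 2 = 48 exceeds the assumed start of 35.

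**Step 4. Simulation under each reading.** Assumptions not in the documents: baseline total 35 (SD 10), worst item starting at 3 or 4, lognormal recovery times (log-SD 0.5), linear or exponential decline, daily noise SD 2, complete data. There are 26 per arm, tested two-sided at 0.05. The planned medians run from symptom onset, so a lag of 0-3 days to Day 1 is allowed at 6 versus 16.

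| Medians | Meaning of response | Slope favours drug | Slope significantly reversed |
|---|---|---|---|
| 6 vs 16 | worst item <=2 | 85-100% | 0% |
| 6 vs 16 | worst item <=1 | 4-92% | 0-2% |
| 6 vs 16 | scores near zero | 0-21% | 0-92% |
| 4 vs 7 | range over all three | 0-44% | 0-52% |

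The mean over Days 2-14, adjusted for the Day-1 score, favours the drug in 88-100% of trials in every row.

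**The case against.** The strongest reply is that the criticised rule is not in the text. A reader might infer that the plan judges symptom benefit by a straight-line slope and will therefore miss or reverse a real effect. The documents do not go that far. Arm is also a main predictor, the interaction is investigated in addition, linear time is never stated for symptoms, and estimand-3 is a difference in scores. If the arm term from a model without the interaction were reported, it would usually show the benefit: a rough check (25 fits per setting, with convergence warnings, scores falling to zero) found it significant in 84-100%. All of this stands. The fault is an unspecified deciding contrast, not a stated wrong one.

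The second reply also stands. On the main definition of response (<=2), the slope does well at the planned 6 versus 16 days and is never reversed, so it cannot be said that the slope lacks power for the plan's own effect. The 4 versus 7 figures come from a trial with a different regimen and outcome.

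The permitted transformation helps only in part. With scores falling to zero, log(1+score) raises correct detection at 6 versus 16 to 55-100%, but at 4 versus 7 it gives 0-49% correct and 0-88% significantly reversed. It is optional, and no offset for zeros is given.

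Finally, Protocol 9.4.1 treats secondary results as hypothesis-generating, recovery time has its own log-rank test, and SAP 7.9 plots the daily scores. These limit the damage but do not say which symptom result is to be reported.

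**Conclusion.** The point holds as a gap in specification with a demonstrable risk. The form of time and the deciding term are not stated, and the one term named for differential behaviour, on its ordinary linear reading, does not rank arms by speed of recovery and does not estimate estimand-3. The non-monotonicity follows from the floor and is plain arithmetic. Its size is uncertain: from almost no loss (response at <=2, 6 versus 16 days) to reversal in most trials (near-zero scores, exponential decline, a few days' lag).

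The percentages rest on the assumed baseline, recovery spread and decline shape. With more dispersed, exponential recovery times both analyses weaken: at 6 versus 16 the slope falls to 58% under the <=2 reading; with scores falling to zero the adjusted mean falls to 82% at 6 versus 16 and 42% at 4 versus 7, where the slope is right in at most 2%. Under all three readings of response the adjusted mean did at least as well as the slope. The change is worth making, though the endpoint is secondary.

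**What to change.** In Protocol 9.4.3 and SAP 5.3.3 Aim-3, keep PROC MIXED but enter day as a categorical factor (arm, day, arm-by-day), with the baseline score as covariate. For the total and each subdomain score, pre-specify one treatment contrast: the arm difference in average score over Days 2-14, with its 95% CI. State that a linear time-by-arm coefficient is not the measure of benefit. This contrast estimates estimand-3 directly.

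The cost is wording only, with the same data and software. The result becomes an average point difference rather than a rate per day, and the model carries more day terms, so the within-participant covariance structure should be named.
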